### **Study Objectives**

Prevention of lung inhomogeneity is an essential part of preventive strategy in neurocritical care, reducing the risks of secondary brain damage from hypoxemia, hypo/hypercapnia or pneumonia. The investigators will examine the effect of lateral tilting (routinely used in critical care) on the lung inhomogeneity that will be analyzed by electrical impedance tomography (EIT). Two types of lateral tilting will be compared: manual positioning of body by nurse versus the bed tilting (15° lateral tilt, original company name (LINET) and product brand name Eleganza 5).

### **Type of study**

1. Monocentric: Neurointensive Care Unit (NICU), Regional Hospital Liberec (research organization);
2. Prospective;
3. Randomized;
4. Intervention: parallel assignment;
5. Blind for statistics: statistics will only know type A or B randomization;
6. Patients: Pilot data in 50 patients, following a statistical evaluation, the study will continue with a total of 200 patients.

### **Entry criteria**

1. Primary brain disease;
2. Hospitalization in NICU, Neurocenter;
3. Age >18 up to 99 years;
4. Unconsciousness;
5. Artificial pulmonary ventilation;
6. Available EIT device.

### **Exclusion criteria**

1. Intracranial hypertension;
2. History of primary lung disease;
3. The terminal stage of the disease;
4. Refractory hemodynamic instability.

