### **The primary aim**

Atelectasis/collapse assessed by EIT or chest x-ray (CXR) at end of observation period.

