### **The secondary aims**

1. Evaluating oxygenation parameters;
2. Evaluating hemodynamic parameters: stroke volume variation (SVV) and cardiac index (CI) in one type of hemodynamic monitor;
3. Comparing staying in Neurocenter Neurointensive Care Unit and cost effectiveness between two groups;
4. Profiling pneumonia incidence between two groups.

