## **Statistical Analysis Plan**

Running statistical analysis will be performed after recruitment of 50 patients. Ventilation distribution in lungs will be evaluated by EIT and in case of non-significant differences in detecting lung inhomogeneity and risk of pneumonia among group 1 and 2, the study will continue.

Complete study analysis will be performed after recruitment of 200 patients.

Continuous variables will be assessed using t-tests or Mann-Whitney tests depending on data distribution. Categorical variables will be assessed using chi-square tests. Multivariate logistic regression analysis will be used estimating the occurrence of pneumonia versus EIT related measures of lung inhomogeneity. For assessing the association between measured oxygenation, EIT derived parameters and ventilator parameters, the Pearson or Spearman correlation method will be used, depending on parameters' distribution.

Liberec, January 7th, 2020

[name]., Ph.D.

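### Patients may enter with pneumonia or lung collapse already present, and neither the endpoints nor the analysis separate disease present at randomisation from later disease

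*Combined protocol and SAP*

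**What the plan says.** Study Objectives gives a preventive rationale, "Prevention of lung inhomogeneity is an essential part of preventive strategy in neurocritical care", and names pneumonia among the risks to be reduced. The same section also states the aim more neutrally, as the effect of lateral tilting on lung inhomogeneity.

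The Entry criteria include "Hospitalization in NICU, Neurocenter" and "Artificial pulmonary ventilation". Neither carries a limit on time since admission or since ventilation began. "Available EIT device" is required, but no baseline EIT or chest film finding is. Among the Exclusion criteria, only "History of primary lung disease" concerns the lungs.

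The primary aim is "Atelectasis/collapse assessed by EIT or chest x-ray (CXR) at end of observation period". It asks for neither new collapse nor change from baseline. Item 4 of the secondary aims is "Profiling pneumonia incidence between two groups", with no case definition, onset rule or at-risk set.

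In the Statistical Analysis Plan, "Categorical variables will be assessed using chi-square tests", with no baseline adjustment or stratification. Risk of pneumonia also enters the evaluation after 50 patients, and a logistic regression relates pneumonia to EIT measures of inhomogeneity. Baseline lung status appears in none of these.

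**The concern.** An unconscious, ventilated patient may already have pneumonia, for example after aspiration, or visible collapse. With no history of primary lung disease, neither condition keeps the patient out. Three analyses are affected.

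- **Pneumonia by arm.** Pneumonia present at randomisation cannot be prevented by either positioning method. If it is counted, it adds events unrelated to treatment to both arms, pulls the risk ratio towards 1 and costs power. The 50-patient evaluation is exposed too, because the study continues when differences, including in risk of pneumonia, are non-significant.
- **Pneumonia versus EIT measures.** Existing pneumonia can itself produce inhomogeneous ventilation. An association could then run from pneumonia to EIT finding, and randomisation does not protect this analysis.
- **Collapse, the primary aim.** A single status when observation ends combines patients who developed collapse with patients who entered with it and did not recover. Prevention and resolution cannot be told apart.

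**Working it through.** **The plan's own figure.** The plan gives 50 pilot patients and 200 in total, without alpha, power, event rates, effect size or allocation ratio. The total cannot be reproduced, so there is no stated power to compare with.

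**Textual check.** Take a patient with pneumonia at randomisation and no earlier lung disease.

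- Entry criteria: nothing about current lung status is asked, so the patient can qualify.
- Exclusion criteria: on an ordinary reading, a history of primary lung disease does not cover pneumonia or collapse acquired with the brain event or on ventilation.
- Secondary aims, item 4: the word incidence points to new cases, but no rule says how this patient is classified.
- Statistical Analysis Plan: no step removes the patient or adjusts for the condition.

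**Illustration for pneumonia.** All inputs are assumptions except the total of 200:

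- 1:1 allocation, so n = 100 per arm; two-sided 5% test;
- new pneumonia r = 30% versus 15% in patients free of it at entry;
- a share q of each arm has pneumonia at entry, and each such patient counts as an event (no resolution).

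Observed risk if entry cases are counted: q + (1 − q)r.

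Power = Φ{[|p1 − p2| − 1.96·√(2p̄(1 − p̄)/n)] / √[(p1(1 − p1) + p2(1 − p2))/n]}, where p̄ is the mean of p1 and p2.

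Restricted to patients free of pneumonia at entry, the risks stay at 30% and 15%, and n falls to 100(1 − q).

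| q | Observed risks if counted | Risk ratio | Power if counted, n = 100 | n per arm if restricted | Power if restricted |
|---|---|---|---|---|---|
| 0% | 30% vs 15% | 0.50 | 72% | 100 | 72% |
| 10% | 37% vs 23.5% | 0.64 | 55% | 90 | 68% |
| 20% | 44% vs 32% | 0.73 | 42% | 80 | 62% |
| 30% | 51% vs 40.5% | 0.79 | 32% | 70 | 57% |

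Worked line, q = 20%, counted: 0.20 + 0.80 × 0.30 = 0.44 and 0.20 + 0.80 × 0.15 = 0.32, so p̄ = 0.38. The null standard error is √(2 × 0.38 × 0.62/100) = 0.0686, and the alternative one is √[(0.2464 + 0.2176)/100] = 0.0681. (0.12 − 1.96 × 0.0686)/0.0681 = −0.21, and Φ(−0.21) is about 0.42. In this case 0.20/0.44 = 45% and 0.20/0.32 = 62.5% of counted events in the two arms would predate randomisation.

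**Chance imbalance at 50 patients.** Entry cases are equal between arms only in expectation. With 25 per arm and q = 20%, two independent binomial counts are exactly equal about 14% of the time and differ by three or more about 37% of the time.

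**Collapse.** The formula above is not applied to the primary aim. Collapse present at entry may resolve, possibly at different rates by arm, so it is not a fixed event.

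**The case against.** The strongest reply is that incidence ordinarily means new cases, and that no sentence instructs anyone to count pneumonia already present. That stands. A reader might infer that the plan, followed as written, counts entry pneumonia as an outcome; the documents do not say so. They leave its handling undefined, and applying the ordinary meaning still needs a record of status at randomisation and a defined at-risk set.

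A reader might also infer that the eligibility rules are wrong and must be tightened. The documents do not support that. The aim is also put as an effect on inhomogeneity, so patients with collapse at entry may carry information on the primary aim, and excluding them would change the target population. The pneumonia problem can be solved without touching eligibility.

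It would also be too strong to call this systematic bias between arms. Randomisation balances entry disease in expectation, so the harm to the arm comparison is dilution plus chance imbalance.

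On size, the 72% in the first row of the table is not what restriction recovers when the total stays at 200. The fair contrast is between the two power columns. Finally, primary lung disease is undefined, and a broad reading might exclude some primary pneumonia, but it would still miss secondary pneumonia and atelectasis.

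**Conclusion.** The concern holds as a gap in endpoint and analysis definition. Entry admits patients with pneumonia or collapse, and nothing in the aims or the Statistical Analysis Plan separates that disease from later disease or adjusts for it.

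For pneumonia, if entry cases are counted, the direction is clear: dilution of the arm comparison, and a regression open to reverse causation. The size is illustrative. On the assumed rates, restriction raises power by about 13, 20 or 25 percentage points (68 − 55, 62 − 42, 57 − 32) at 10%, 20% or 30% with pneumonia at entry. The true share and the true event rates are not in the documents.

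For collapse, the conclusion is one of interpretation and no figure is attached: the primary measure mixes prevention with resolution. This should be corrected, because the change is small and keeps the randomised comparison.

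**What to change.** 1. **Pneumonia** (secondary aims, item 4, and Statistical Analysis Plan). Count only pneumonia first diagnosed after randomisation. Restrict the arm comparison, including its use at 50 patients, and the logistic regression to patients without pneumonia at randomisation, judged from existing pre-randomisation records. Because this status is fixed before allocation, the comparison remains randomised.
2. **Collapse** (primary aim and Statistical Analysis Plan). Record collapse status at randomisation, from the EIT device already required at entry or from an existing chest film, and adjust for or stratify by it. Item 1 alone does not cover the primary endpoint.
3. **Eligibility.** Whether to exclude known disease at entry, or to limit time on ventilation before randomisation, is optional and left to the sponsor.

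Cost: changes of wording, and a smaller pneumonia analysis set (90, 80 or 70 per arm in the illustration). The plan schedules no baseline EIT recording or film, so item 2 may need one EIT recording before randomisation where no suitable film exists.

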### **The primary aim**

Atelectasis/collapse assessed by EIT or chest x-ray (CXR) at end of observation period.

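### The objective and the 50-patient check rest on EIT lung inhomogeneity, but the primary aim is atelectasis/collapse, and inhomogeneity is not listed as any aim

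*Combined protocol and SAP*

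**What the plan says.** The Study Objectives section says that the investigators will study the effect of lateral tilting on "the lung inhomogeneity that will be analyzed by electrical impedance tomography (EIT"), comparing nurse positioning with bed tilting.

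The primary aim section names one outcome, "Atelectasis/collapse assessed by EIT or chest x-ray (CXR"), read when observation ends.

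The secondary aims are four:
- "Evaluating oxygenation parameters"
- haemodynamics, given as "stroke volume variation (SVV) and cardiac index (CI) in one type of hemodynamic monitor"
- "Comparing staying in Neurocenter Neurointensive Care Unit and cost effectiveness between two groups"
- "Profiling pneumonia incidence between two groups"

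The Statistical Analysis Plan provides for an analysis after 50 patients, at which the EIT ventilation distribution is evaluated, and sets this rule: "in case of non-significant differences in detecting lung inhomogeneity and risk of pneumonia among group 1 and 2, the study will continue". The complete analysis follows at 200 patients. EIT inhomogeneity measures then appear in a logistic regression for pneumonia, and EIT parameters in correlation analyses. Atelectasis and collapse are not mentioned in that section.

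**The concern.** A primary outcome should be the quantity that the objective asks about, and a decision on whether to go on should normally rest on it or on something with a stated relation to it. Here the objective and the continuation rule refer to inhomogeneity, while the primary aim refers to collapse. Collapse is one possible cause of uneven ventilation. The documents do not say that the two are the same.

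Two things are at stake. First, a positive or null result on collapse at 200 patients would give no primary answer about inhomogeneity. If inhomogeneity were then reported as the main finding, it would be a variable never listed as an aim. Second, a difference in inhomogeneity or pneumonia at 50 patients could end the study before the primary aim has been assessed at the planned size.

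**Working it through.** **Step 1. The sections side by side.**

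| Section | EIT inhomogeneity | Atelectasis/collapse | Pneumonia |
|---|---|---|---|
| Study Objectives | the effect to be studied | not named | named only as a risk to be reduced |
| The primary aim | not named | the outcome, by EIT or CXR | not named |
| The secondary aims | not named | not named | item 4 |
| SAP, rule at 50 patients | decides continuation | not named | decides continuation |
| SAP, complete analysis | related to pneumonia in a regression; EIT parameters in correlations | not named | outcome of that regression |

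The first column is filled in the objective and the SAP and empty in both lists of aims. The second is filled only in the primary aim.

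**Step 2. Could the terms be one variable under two names?** The documents define no EIT index, no threshold that turns an EIT reading into collapse, and no rule linking the two terms. The primary aim also accepts a chest x-ray, so it could be decided without the EIT measurement that the objective names. On the text, they are two variables.

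**Step 3. What the rule at 50 patients does.** The SAP says when the study continues and leaves unstated what follows otherwise; the natural reading is that a significant difference can end it. The plan gives no significance level. Assume each of the two variables is tested at two-sided 0.05, the tests are independent, and there is no true difference:
- If significance on either one ends the study: 1 − (1 − 0.05)² = 0.0975, or 9.75%.
- If both must be significant: 0.05² = 0.0025, or 0.25%.

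The wording permits either reading. Dependence between the tests would change both figures. In each case collapse plays no part in the decision.

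**Step 4. What happens once the check and the primary aim share a variable.** The same outcome is then tested at 50 and at 200 patients. With information proportional to patients, the two test statistics have correlation √(50/200) = 0.5. Overall type I error is P(|Z₁| > c₁ or |Z₂| > c₂) for a bivariate normal with that correlation:
- 0.05 at both looks (c₁ = c₂ = 1.96): 0.091, or about 9%.
- For illustration, 0.001 at 50 and 0.05 at 200: 0.0506.
- For illustration, 0.001 at 50 and 0.049 at 200: 0.0496.

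A strict first look therefore costs almost nothing at the final analysis.

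**Step 5. Sample size.** The total of 200 cannot be reproduced for either variable. The plan states no significance level, power, effect size, standard deviation or event rate, so the sample size does not show which variable was meant as primary.

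**The case against.** The best defence is that this is a missing link between terms and not a wrong endpoint. The objective states a broad construct, the primary aim gives a concrete finding that EIT can show, and the SAP speaks of detecting inhomogeneity, which could mean a yes/no finding. Collapse may be the intended working form of inhomogeneity. The documents do not exclude this, but they do not say it either, and the chest x-ray alternative fits it poorly. If that is the intention, one defining sentence would settle most of the point.

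It is also fair that an interim decision may rest on a related or earlier variable without error. That needs a stated reason, and none is given.

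Three stronger readings are tempting and not supported:
- A reader might infer that the objective, the primary aim and the check use three different variables. They do not: the objective and the check share inhomogeneity, and the pneumonia part of the check is a listed secondary aim. Only the primary aim stands apart.
- A reader might infer that inhomogeneity goes unanalysed. The SAP has tests for continuous variables, the regression and the correlations. What is missing is its place among the aims.
- A reader might want to put a figure on the information lost by scoring collapse as present or absent. That calculation holds only if collapse is a cut of the same EIT measure. The documents do not say so, a chest x-ray reading is not such a cut, and the primary aim does not state how collapse is scored.

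**Conclusion.** The point holds in this form: the quantity in the objective and in the continuation rule is not an aim at any level, and the primary outcome has no part in the continuation rule. The primary result would not answer the stated objective, and the study could end at 50 patients on non-primary variables. That second consequence assumes that a significant difference means not continuing, which the SAP implies but does not spell out.

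The mismatch itself needs no calculation. The figure of about 9% describes two unadjusted looks at one variable, at an assumed two-sided 0.05. It is the reason to adjust once the sections are aligned; it is not an error rate of the present plan for collapse, which the rule at 50 patients does not test. The documents do not settle which variable should be primary. That is the sponsor's choice.

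**What to change.** Use one variable in the Study Objectives, the primary aim and the rule at 50 patients. There are two ways.

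(a) Keep atelectasis/collapse as primary. Restate the objective and the 50-patient check in terms of collapse, limit the main conclusion to it, and add EIT inhomogeneity to the secondary aims.

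(b) If inhomogeneity is the intended question, name one numerical EIT inhomogeneity measure as primary, compare it between groups with the t-test or Mann-Whitney test already in the SAP, and move collapse to the secondary aims.

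In either case, base the 50-patient decision on the primary variable, state what follows a significant result as well as a non-significant one, and fix in advance a stricter significance level for that look. Pneumonia stays a secondary aim; if it is to keep a role in the decision, the SAP should say what role and why.

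The cost is changes of wording and a slightly stricter threshold. Under (b) the headline result becomes an index and not a clinical finding, and the index has yet to be named. The entry criteria require only that an EIT device be available and no EIT schedule is given, so (b) also requires confirming that EIT will be recorded in every patient at the time of the primary assessment.

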### **The secondary aims**

1. Evaluating oxygenation parameters;
2. Evaluating hemodynamic parameters: stroke volume variation (SVV) and cardiac index (CI) in one type of hemodynamic monitor;
3. Comparing staying in Neurocenter Neurointensive Care Unit and cost effectiveness between two groups;
4. Profiling pneumonia incidence between two groups.

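### Cost effectiveness is a secondary aim, but no planned analysis relates cost to effect, and the one rule that could cover cost would send skewed costs to a rank test rather than a comparison of means

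*Combined protocol and SAP*

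**What the plan says.** The secondary aims, item 3, combines two comparisons: "Comparing staying in Neurocenter Neurointensive Care Unit and cost effectiveness between two groups". No cost item, costing perspective or measure of effectiveness is named for it.

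The Statistical Analysis Plan does not mention cost. It lists four kinds of analysis:

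- continuous variables: "Continuous variables will be assessed using t-tests or Mann-Whitney tests depending on data distribution";
- categorical variables: "Categorical variables will be assessed using chi-square tests";
- pneumonia: "Multivariate logistic regression analysis will be used estimating the occurrence of pneumonia versus EIT related measures of lung inhomogeneity";
- association between oxygenation, EIT-derived and ventilator parameters: "the Pearson or Spearman correlation method will be used, depending on parameters' distribution".

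On size, the Type of study section has "Pilot data in 50 patients, following a statistical evaluation, the study will continue with a total of 200 patients" and describes the design as "Intervention: parallel assignment". The allocation ratio, significance level and sidedness are not stated.

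**The concern.** A cost-effectiveness comparison needs two things: the difference in mean cost between arms, and that difference set against a difference in effect with their joint uncertainty. The mean matters because mean cost times number of patients is what the unit pays. A few very long stays count in full towards that total, but hardly move a comparison of ranks.

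The plan supplies neither. Under either branch of the continuous-variable rule, cost is at most compared alone. If costs are right-skewed, as intensive-care costs usually are, the rule points to Mann-Whitney, which asks which arm tends to have the lower value for a typical patient. The choice at stake is between a tilting bed and nurse positioning, and a rank result read as a cost result could misinform it.

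**Working it through.** **What follows from the text alone.** Take the listed analyses in turn. Chi-square is for categorical variables. The logistic model has pneumonia as its outcome. The correlations are confined to oxygenation, EIT and ventilator parameters. Only the t-test or Mann-Whitney rule can apply to a per-patient cost, and it does not involve an effect measure. This needs no assumption.

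**What the rank test would do.** The plan has no cost figure to reproduce, so this part is illustrative.

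Inputs from the documents: 200 patients in two parallel groups. Assumed: 1:1 allocation (200 / 2 = 100 per arm), two-sided 5%, lognormal cost with log-mean μ and log-SD s.

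Formulas:

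- mean = median × exp(s²/2);
- Mann-Whitney responds to P(B < A) = Φ((μA − μB) / √(sA² + sB²)). The term s²/2, which raises the mean, does not enter the numerator.

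*Which branch applies.* The plan names no normality check. With Shapiro-Wilk as an assumed screen, normality is rejected in at least 99.8% of lognormal samples of 100 at log-SD 0.5 or more.

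*Unequal spread, log-SD 0.6 (A) versus 1.0 (B); √(0.36 + 1.00) = 1.166.*

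- (a) Equal medians of 10. Means are 10 × exp(0.18) = 11.97 and 10 × exp(0.50) = 16.49, ratio 1.38. P(B < A) = Φ(0) = 0.50. Mann-Whitney rejects in 5.4% to 6% of simulated trials; a Welch comparison of means on the same data rejects in 53%.
- (b) Equal means. The log-mean difference is −(0.50 − 0.18) = −0.32, so B's median is exp(−0.32) = 0.73 of A's, 27% lower. P(B < A) = Φ(0.32 / 1.166) = 0.61. Mann-Whitney rejects in about 76%.
- (c) B's median 20% lower. Mean ratio 0.80 × exp(0.32) = 1.10. P(B < A) = Φ(0.223 / 1.166) = 0.58. Mann-Whitney rejects in 45% to 47%, in favour of B, the costlier arm. In 22% of trials it does so although B's observed sample mean is also the higher one.

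*Milder difference in spread, 0.6 versus 0.8.* At equal medians the mean ratio is exp((0.64 − 0.36) / 2) = exp(0.14) = 1.15, and the test rejects in 5% to 6%. At equal means it rejects in 27% to 29%.

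*Equal spread, B's mean 38% higher.*

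- Log-SD 0.8 in both arms: Mann-Whitney identifies the costlier arm in 77% to 79%, Welch in 68%.
- Log-SD 1.0 in both arms: 60% and 44%.
- Significance in the wrong direction: 0.0% in both. For a mean only 10% higher it stays below 1%.

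Ranges show the spread between repeated simulations of 3,000 to 5,000 trials each.

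**The case against.** The plan never assigns cost to Mann-Whitney. Getting there takes three steps that it does not supply: cost falls under the general sentence on continuous variables, cost in this unit is right-skewed, and the distribution-based choice is made by something like a normality test. With about 100 per arm, a statistician could defend a t-test under the same sentence. This stands as a limit on the second half of the point. It does not touch the first half, because the t-test branch would still leave cost unrelated to effect.

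A reader might infer that the plan is likely to call the costlier arm cheaper. The documents do not support that. Every adverse scenario above gives the arms different spreads, and nothing in the documents says the two positioning methods differ in cost spread. With equal log-spread Mann-Whitney finds the costlier arm more often than a t-test does. Unequal spread is conceivable, for example if positioning changed pneumonia incidence and with it the long stays, but that is inference.

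A reader might also infer that all of item 3 is undeliverable. It is not: NICU stay can be compared by Mann-Whitney as a comparison of distributions.

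Finally, the mean-based alternative is not powerful. In the same scenarios a percentile bootstrap interval for the mean difference shows the costlier arm as costlier in only about 62% of trials in (a), 9% in (c), and 22% in the milder version of (a). It targets the right quantity but will often be inconclusive. That stands, and it should be stated with the fix.

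**Conclusion.** The concern holds in a conditional form. From the text alone: cost effectiveness is a stated aim, and no listed analysis joins cost to effect. If costs are right-skewed and the general rule is followed, cost goes to a test that does not compare mean cost.

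How much damage this does depends on assumptions. With lognormal cost, 100 per arm and log-SD 0.6 versus 1.0, Mann-Whitney detects a 38% higher mean at equal medians no more often than chance (about 5%). It favours an arm whose mean is 10% higher and median 20% lower in about 47% of trials. With equal log-spread neither failure appears. The documents give no cost data to say which case applies, so these percentages illustrate a risk and do not forecast this trial's result.

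The plan should be amended. The matter affects half of one secondary aim and does not touch the primary aim.

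**What to change.** In the Statistical Analysis Plan section:

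1. Exempt cost from the distribution-based choice of test.
2. Name the cost items, restricted to those the unit already records, for example NICU days multiplied by a unit cost. The documents do not say that nurse time or unit costs are collected, so including nurse positioning time would mean new data collection.
3. Compare arithmetic mean cost per patient, as randomised, with a bias-corrected or t-type bootstrap 95% confidence interval. A plain percentile interval covered only 91% to 95% in the unequal-spread scenarios.
4. Name one effect already planned, either pneumonia or the primary outcome. Resample it jointly with cost and report the joint cost and effect difference as an incremental ratio or net benefit. Net benefit is the steadier choice if the effect difference may be near zero.
5. Keep Mann-Whitney for NICU stay if wanted, described as a comparison of distributions.

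The cost is SAP wording, a costing definition and a short bootstrap program. The price in precision is a wide and often inconclusive interval on mean cost. If cost data are not available, delete the cost-effectiveness wording from item 3 and claim only a comparison of stay. No treatment, schedule or recruitment change is involved.
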